In addition to the potential harm SARS-CoV-2 infection may cause to HCWs, it will reduce healthcare capacity at a time when it will be overstretched by severe COVID-19 cases. In the context of the paradigm of “flattening the curve” to reduce peak infections to below the ceiling capacity of the healthcare system, infection of HCWs will lower the ceiling capacity making it less likely that systemically meaningful reductions can be achieved.

Understanding infection in HCWs is fundamental to informing specific infection prevention and control measures needed to protect HCWs.¹ Relatedly, characterizing the risk and the related risk factors in HCWs exposed to SARS-CoV-2, and quantifying the association of potential prophylactic treatments (medications or treatments designed and used to prevent occurrence of SARS-CoV-2 infection) with reduced risk of COVID-19 is a high priority globally. Several registries have been developed in the US and Europe, but low- and middle-income countries are underrepresented at this time.¹⁴

An international registry of HCWs exposed to SARS-CoV-2 will provide fundamental information on the status and give an indication of the association of potential prophylactic and preventive measures. In addition, this registry could also be used to inform study rationales and designs for future research involving COVID-19 among HCWs. Furthermore, registry findings may also inform recommendations and policies on the prophylactic use of potential therapies in HCWs.

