8.3.5 Other Covariates

- COVID-19 symptoms (and date the symptoms begin)
 - Fever (temperature over 38°C)
 - Subjective fever (felt feverish)
 - Chills
 - Myalgia (muscles hurt or ache)
 - Rhinorrhea (runny or drippy nose)
 - Pharyngitis (sore throat)
 - Cough (new onset or worsening of chronic cough)
 - Dyspnea (hard to breathe or difficulty breathing)
 - Pneumonia
 - Nausea or vomiting
 - Headache or migraine
 - Abdominal pain (pain in tummy)
 - Asthenia (weakness or loss of strength)
 - Arthralgia (joint pain)
 - Anosmia (loss of smell)
 - Ageusia (loss of taste)
 - Blue coloring in toes
 - Diarrhea (two or more looser-than-normal stools in 24 hours)
- SARS-CoV-2 testing
 - Type of test, if known
 - PCR (positive/negative)
 - Antigen test (positive/negative)
 - Serology (immunoglobulin G [IgG] and/or immunoglobulin M [IgM], positive/negative or titer)
 - Date of test

- Household history (COVID-19)
 - Number of household contacts
 - Additional household member(s) exposed to COVID-19 (yes/no). If yes, how many?
 - Additional household member(s) with symptoms consistent with COVID-19 (yes/no). If yes, how many?
 - Additional household member(s) diagnosed with COVID-19 (yes/no). If yes, how many?
- Healthcare worker-level covariates
 - Demographics at entry
 - Underlying conditions and key co-morbidities
 - Job characteristics
 - Concomitant medications
 - Blood type
- Healthcare facility characteristics
 - Country, region
 - Urban or rural setting
 - Type of facility (public/private/community healthcare)
 - Teaching/university hospital or non-teaching
 - Capacity
 - number of patients tested for COVID-19
 - number of COVID-19 patients treated
 - number of hospitalized beds (overall, ICU, emergency department)
 - number of exposed HCWs
 - number of HCWs tested for COVID-19
 - Number of HCWs who developed confirmed or clinically diagnosed COVID-19
 - Number of HCWs who died from COVID-19
 - Approved PPE use policy, and experience of PPE shortage
 - Approved prophylactic treatment policy
 - Shortage of COVID-19 related tests
 - BCG vaccination policy
- Concomitant medications (other than for COVID-19)
 - Antibiotics (yes/no). If yes, please specify.
 - Azithromycin
 - Trimethoprim/sulphamethoxazole
 - Macrolide antibiotics (roxithromycin, clarithromycin, erythromycin)

- Other antibiotics
- Antimalarials (yes/no). If yes, please specify.
 - Hydroxychloroquine
 - Chloroquine
 - Sulfadoxine-pyrimethamine (SP)
 - Other antimalarials

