Pneumonia	X	X	-
Nausea or vomiting	X	X	-
Headache or migraine	X	X	-
Abdominal pain (pain in tummy)	X	X	-
Asthenia (weakness or loss of strength)	X	X	-
Arthralgia (joint pain)	X	X	-
Anosmia (loss of smell)	X	X	-
Ageusia (loss of taste)	X	X	-
Blue coloring in toes	X	X	-
Diarrhea (two or more looser-than-normal stools in 24 hours)	X	X	-
SARS-CoV-2 testing			
Tested? (yes/no)	X	X	-
Type of test	X	X	-
PCR (positive/negative)	X	X	-
Antigen test (positive/negative)	X	X	-
Serology (IgG and/ or IgM, positive/negative or titer)	X	X	-
Date of test	X	X	-
Serology testing	X	X	-
Household history (COVID-19)			
Number of household contacts	X	X	-
Additional household member(s) exposed to COVID-19 (yes/no) If yes, how many?	X	X	-
Additional household member(s) with symptoms consistent with COVID-19 (yes/no) If yes, how many?	X	X	-
Additional household member(s) diagnosed with COVID-19 (yes/no) If yes, how many?	X	X	-
Underlying conditions and key morbidities			
Chronic lung disease	X	-	-
Diabetes mellitus	X	-	-
Cardiovascular (heart) disease	X	-	-
Chronic renal (kidney) disease	X	-	-
Chronic liver disease	X	-	-
Immunocompromised condition (HIV/AIDS, organ transplant, other)	X	-	-
Tuberculosis	X	-	-
Neurologic/neurodevelopmental	X	-	-
Hypertension (high blood pressure)	X	-	-
History of stroke	X	-	-
Other chronic diseases	X	-	-
If female, currently pregnant	X	-	-
If female, currently breastfeeding/lactating	X	-	-
Job characteristics			
Type of healthcare work	X	-	-

Primary work location (ED, ICU, Medical floor)	X	X	-
Number of hours with patients	X	X	-
Concomitant medications (other than for COVID-19)			
Antibiotics (yes/no)	X	X	-
Antimalarials (yes/no)	X	X	-
Antiparasitics (yes/no)	X	X	-
Antiretrovirals for HIV (yes/no)	X	X	-
Antivirals (yes/no)	X	X	-
Medication for high blood pressure and cardiovascular disease (yes/no)	X	X	-
Nonsteroidal Anti-inflammatory Drugs (NSAIDs) (yes/no)	X	X	-
Botanicals (yes/no)	X	X	-
Immunocompromising drugs (yes/no)	X	X	-
COVID-19 vaccine (to be selected as applicable)			
Convidicea (Ad5-nCoV)	X	X	
CoronaVac (Sinovac)	X	X	
Covaxin (BBV152)	X	X	
EpiVacCorona (Vector Institute)	X	X	
Janssen Pharmaceuticals (Johnson & Johnson) (Ad26.COV2.S)	X	X	
Moderna COVID-19 Vaccine	X	X	
Novavax (NVX-CoV2373)	X	X	
Oxford-AstraZeneca COVID-19 Vaccine	X	X	
Pfizer-BioNTech COVID-19 Vaccine	X	X	
Sinopharm BBIBP-CorV	X	X	
Sputnik V COVID-19 Vaccine	X	X	
Other (please specify)	X	X	

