3.5.2 Secondary Outcomes

For the following outcomes, infection status will be defined as per the composite primary outcome. Ambulatory status and hospitalisation will be based on responses to the relevant questions in the survey. Mortality will be based on the survey response of each subject's secondary contact. Prophylactic treatment will be based on relevant questions from healthcare worker's surveys.

- Occurrence of SARS-CoV-2 uninfected HCWs
- Occurrence of SARS-CoV-2 infection with ambulatory status and no limitation of activities. This will be defined as subjects reporting COVID-19 related symptoms, clinical diagnosis of COVID-19 or positive test results but reporting "No" limitation of activities due to their symptoms and no hospitalisation.
- Occurrence of SARS-CoV-2 infection with ambulatory status and limitation of activities. This will be defined as subjects reporting COVID-19 symptoms, clinical diagnosis of COVID-19 or positive test results and reporting "Yes" to having their usual activities limited being limited due to their symptoms, but no hospitalisation.
- Occurrence of hospitalisation due to COVID-19 illness with mild disease. This is defined as being hospitalised without being admitted to the ICU or without ventilation
- Occurrence of hospitalization due to COVID-19 illness with severe disease. This is defined as being hospitalised with either admittance to the ICU and/or receiving ventilation.
- Occurrence of all-cause mortality

- Type of prophylactic treatments (Chloroquine, Hydroxychloroquine, Azithromycin, Lopinavir/ritonavir, Ivermectin, others) by dose, frequency and duration, overall and by country/region/site. To note, prophylactic treatment use will be defined by relevant indication from 'prophylactic treatment' section of the survey; in addition, if there is an indication of drugs in 'concomitant medications' section that are also listed but not selected under 'prophylactic treatment' section, those indications will be added too.

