 - Other antiparasitics
- Antiretrovirals for Human Immunodeficiency Virus (HIV) (yes/no). If yes, please specify.
 - Lopinavir
 - Ritonavir
 - Tenofovir
 - Nelfinavir
 - Other antiretrovirals
- Antivirals (yes/no). If yes, please specify.
 - Oseltamivir
 - Favipiravir
 - Arbidol
 - Anti-hepatitis C treatments
 - Remdesivir
 - Other antivirals
- Medication for high blood pressure and cardiovascular disease (yes/no). If yes, please specify.
 - Angiotensin-converting enzyme (ACE) inhibitor (e.g. lisinopril, enalapril)
 - Angiotensin II receptor blockers (ARB) inhibitor (e.g. losartan, irbersartan)
 - Other anti-hypertensive for high blood pressure
 - Other medicine for high blood pressure and cardiovascular disease (E.g. antiarrhythmics, inotropes, chronotropes)
- Nonsteroidal Anti-inflammatory Drugs (NSAIDs) E.g. Aspirin, Ibuprofen, Indomethacin, Celecoxib, Diclofenac (yes/no).
- Botanicals-- Artemisia teas (COVID Organics) (yes/no)
- Immunocompromising drugs such as corticosteroids, cancer chemotherapy, cyclosporine, colchicine, drugs for autoimmune conditions such as lupus, rheumatoid arthritis or Crohn's disease (yes/no)
- Changes in concomitant medications

Any prophylactic medications that are indicated as concomitant medications being taken by HCWs will be considered during analysis as part of a prophylactic treatment. This will apply to the following prophylactic medications:

- Hydroxychloroquine
- Chloroquine
- Azithromycin
- Lopinavir/ritonavir
- Ivermectin

4 Data security/privacy

- The Application has received a full penetration test from an accredited third party to cover cyber security threats.
- Data is segregated between the collection nodes and analysis nodes. Only information technology support staff have access to the data in the nodes for the express purposes of server support.
- All data on the analysis platform is tokenized with a unique patient token generated on the node. This tokenization uses a powerful salted hash algorithm (a document explaining this process may be reviewed if necessary but cannot be released for security reasons).
- Access to the data platform is controlled by Azure Active Directory accounts managed by the Parexel Support team.
- Access to the Application can only be achieved by end user registration using a set of industry leading authentication providers.
- The application has a unidirectional data flow from the node to the analysis platform so there is no risk of horizontal escalation issues.

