6.4 Primary analysis

6.4.1 Frailty model: mixed effect Cox regression

For the time to COVID-19 infection outcome, both crude and adjusted hazards ratios will be estimated for time to COVID-19 infection with respect to prophylaxis use. The primary objective of this analysis is to assess the association between prophylactic treatments and the reduced risk of SARS-CoV-2 infection in HCWs caring for COVID-19 patients. A mixed effect Cox regression model (ie. frailty model) will be used to estimate adjusted hazard ratios. This method will allow the utilization of both the repeated measures gathered from each HCWs surveys, as well as the incorporation of time-varying covariates of interest such as PPE usage and COVID-19 exposure. Each subject will be included as a random effect. Both time-fixed and time-varying covariates will be included in the model. Covariates will be assessed using a univariate model, any covariates with a p-value less than 0.20 will be included in a multivariate model. A backward stepwise process will then be completed, where the covariates with largest p-value are removed one at a time until all covariates that remain are significant at the 0.10 level. The time-fixed covariates, healthcare facility and country will be included in the model regardless of their significance level. Including the healthcare facility and country covariates will make each healthcare worker's COVID-19 outcome conditionally independent on the background COVID-19 incidence occurring within each subject's healthcare facility and country. A list of additional covariates to be considered can be found in Table 5.4.1. For each subject in the control group, the index date (ie. time of first known exposure to COVID-19 patients) will be used as time zero. For HCWs that are treated with prophylaxis at any time their index date will be 7 days after initiation of treatment. Having an index date near treatment initiation will prevent the introduction of survivorship bias into the analysis.

Table 5.4.1 Model Covariates

Time-fixed/Time-varying Covariate	Covariate Name
Time-fixed Covariates	Healthcare facility, Country, Age, Biological Gender, BMI, Smoking status, Ethnicity, Blood type, Primary work location, Type of healthcare worker, Medical history

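### Listed drugs reported only as non-COVID-19 concomitant medication are counted as prophylaxis in the main exposure, with no scheduled start date and no planned analysis that separates them

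*SAP*

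**What the plan says.** **The rule.** SAP 3.6.5: "Any prophylactic medications that are indicated as concomitant medications being taken by HCWs will be considered during analysis as part of a prophylactic treatment". Five drugs are named: hydroxychloroquine, chloroquine, azithromycin, lopinavir/ritonavir and ivermectin. SAP 3.5.2 and 6.5 say the same of the case "if there is an indication of drugs in 'concomitant medications' section that are also listed but not selected under 'prophylactic treatment' section": those reports are added to prophylactic use.

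**What the concomitant section is.** Protocol 8.3.5 and SAP 3.6.5 list these drugs under a heading that opens "Concomitant medications (other than for COVID-19". SAP 6.3.6 tabulates the same drugs as medication for purposes unrelated to COVID-19.

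**What the protocol calls prophylaxis.** Protocol section 6 explains potential prophylactic treatments as "medications or treatments designed and used to prevent occurrence of SARS-CoV-2 infection".

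**What the primary model needs.** SAP 6.4.1 says that for workers treated with prophylaxis at any time "their index date will be 7 days after initiation of treatment". Controls start at first known exposure to a COVID-19 patient.

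**What is collected.** Protocol 8.3.2 and Appendix 2 schedule start date, stop date, dose and duration for prophylactic treatments. For concomitant drugs, Appendix 2 has rows such as "Antimalarials (yes/no", at enrollment and weekly. Protocol 8.3.5 asks for the drug to be specified, and SAP 3.6.5 adds "Changes in concomitant medications". No date, dose or duration field is listed.

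**The concern.** Prophylaxis use is the exposure in the primary objective. The rule adds people whose reason for taking the drug was, by the survey's own heading, something else. Three problems follow.

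- **Confounding by the other indication.** A worker taking lopinavir/ritonavir for HIV or hydroxychloroquine for autoimmune disease may differ from controls in infection risk for reasons unrelated to prophylaxis.
- **Protopathic bias.** Azithromycin taken for early, undiagnosed COVID-19 symptoms would be recorded as prophylaxis just before the infection is recorded. Protocol 8.9 and SAP 7.6 warn of this mechanism.
- **Timing.** The model places each treated worker by an initiation date that is not scheduled for these reports.

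The result would be a hazard ratio for a mixture of preventive and other use, with no analysis showing how far the mixture matters.

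**Working it through.** **1. Can time zero be set for the added users?**

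- *Already on the drug at enrollment.* The enrollment survey shows current use, not when it began. Time zero is undefined. Where first exposure to patients preceded enrollment, drug status in that interval is also unknown. The partial-date rule in SAP 6.2.1 needs at least a year, so it does not help.
- *Starting during follow-up.* The first weekly survey reporting the drug places the start to about a week, or longer if surveys were missed. That uncertainty is as long as the 7-day lag itself.

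**2. Does a planned analysis isolate these users?**

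- SAP 6.6 subgroups: COVID-19 status at entry, PCR-confirmed absence of infection at index date, serology available, and time from index date to entry. None separates them.
- SAP 6.7: alternative outcome definitions, and drop-outs counted as events. Neither separates them.
- Table 5.4.1: concomitant medication is not a candidate covariate. Medical history is, but p-value selection can drop it.
- SAP 7.5 relies on inverse probability weighting in a section 5.4.2. SAP 6.4 contains only the frailty model.

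**3. Reproducing the plan's power.** Inputs from SAP section 5 and Protocol 8.7.7: N = 10,000, 20% unexposed (2,000 against 8,000), 10% risk in the unexposed, RR 0.78, 80% power; two-sided 5% from SAP 6.1.

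- Events D = 2,000 × 0.10 + 8,000 × 0.078 = 200 + 624 = 824.
- Schoenfeld: power = Φ(√(D·q·(1−q)) × |ln HR| − 1.96), with q = 0.20.
- √(824 × 0.16) = 11.48; |ln 0.78| = 0.2485; Φ(11.48 × 0.2485 − 1.96) = 81.4%.

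This agrees with the stated 80% to within 2 points. The plan does not name its method; a pooled two-proportion test gives 87.7%.

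**4. Effect of relabelling non-users.** Let a and b be the shares of infected and uninfected true non-users who report a listed drug as concomitant medication. The documents give neither, so both are assumptions. Of 2,000 non-users, 200 are infected and 1,800 are not.

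- Observed risk in non-users = 200(1−a) / [200(1−a) + 1,800(1−b)].
- Observed risk in users = (E + 200a) / (8,000 + 200a + 1,800b), with E = 624 for a true RR of 0.78 and E = 800 for 1.00.

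| a | b | Moved | True RR 0.78 becomes | Power | True RR 1.00 becomes |
|---|---|---|---|---|---|
| 5% | 5% | 100 | (634/8,100)/(190/1,900) = 0.783 | 79% | 1.00 |
| 10% | 10% | 200 | (644/8,200)/(180/1,800) = 0.785 | 76% | 1.00 |
| 20% | 20% | 400 | (664/8,400)/(160/1,600) = 0.790 | 70% | 1.00 |
| 10% | 5% | 110 | (644/8,110)/(180/1,890) = 0.834 | 53% | 1.06 |
| 20% | 2% | 76 | (664/8,076)/(160/1,924) = 0.989 | 3% | 1.25 |

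The power column uses the Schoenfeld formula with D = 824, the observed RR and the observed unexposed share.

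**5. A second reading: dilution of the labelled users.** Suppose a share c of the 8,000 labelled exposed are other-indication users with no protection. Observed RR = 0.78(1−c) + c. For c = 5% this is 0.791 (power 77%); for c = 30% it is 0.846 (power 51%). The documents do not give c either.

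**The case against.** The best defence is that the SAP is entitled to this choice. The words in Protocol section 6 are a parenthesis in the background. Protocol 8.3.2 and Appendix 3 set no test of intent, and Protocol 8.7.1 leaves exposure variables to the SAP. If the question is whether the drug itself lowers risk, someone taking hydroxychloroquine for another reason is exposed, and leaving that person among the controls would also misclassify. All of this stands. A reader might infer that the SAP breaches a binding protocol definition; the documents do not support that. They show an unexplained departure in a delegated choice.

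Second, a reader might infer that time zero cannot be set for any of these users. That is too strong. Weekly reports name the drug and record changes, so starts during follow-up can be placed roughly. The gap is at its clearest for use already under way at enrollment.

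Third, safeguards exist. Medical history, which includes immunocompromised conditions, is a candidate covariate. The subgroups by COVID-19 status at entry and by PCR-negative status at index date bear on protopathic bias, as does the 7-day lag where a start can be placed. Azithromycin entered in the prophylaxis section would carry the same bias, so the rule does not create the problem. These points reduce the concern. None of the safeguards removes azithromycin started for undiagnosed symptoms during follow-up, and none compares results with and without the added users.

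Finally, the large shifts depend wholly on infected non-users reporting these drugs 2 to 10 times as often as uninfected ones (10% against 5%, up to 20% against 2%). Nothing in the documents supports any particular ratio. That stands too.

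**Conclusion.** The point holds as a should-fix. As written, the plan mixes other-indication users into the main exposure without justification. Time zero is undefined for those already on the drug at enrollment and approximate for later starters, and no planned analysis tests the choice.

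The size and direction of the bias cannot be determined from the documents. With equal reporting of 5-20% in infected and uninfected non-users, the bias is negligible: a true RR of 0.78 becomes 0.783-0.790 and 1.00 stays 1.00, although power falls from 81% to 79-70%. With 10-20% of infected against 2-5% of uninfected non-users reporting, 0.78 becomes 0.83-0.99 and 1.00 becomes 1.06-1.25. The second range shows what differential reporting could do and does not predict what will happen.

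A reader might also infer that the dose-and-duration secondary objective is corrupted. The documents support less: SAP 6.2.1 reports missing values as missing, so the consequence is incomplete dose and duration data for the added users.

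**What to change.** In SAP 3.5.2, 3.6.5 and 6.5:

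1. Define the primary exposure from the prophylactic-treatments section only, with its recorded start date.
2. Place workers who report a listed drug only as concomitant medication in a separate exposure category, time-varying from the enrollment and weekly reports. They are then neither prophylaxis users nor plain controls.
3. Report the combined any-use definition as a sensitivity analysis. State how time zero is set when no start date exists, separately for use already under way at enrollment and for starts during follow-up.
4. Report how many workers fall in the separate category, by drug and infection status, so that readers can judge whether reporting was differential.

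The cost is SAP wording and one extra model, using data already collected. The downside is slightly fewer workers classed as exposed in the primary analysis. The broader pharmacological question is still answered by the sensitivity analysis.

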6.1 Overview

All statistical analyses will be conducted using R (version 1.3.1093), unless otherwise specified.

For all descriptive analyses, categorical variables will be summarized by number of observations and percentage (%). Percentages will be rounded to one decimal place and will be based on available observations (known values), unless otherwise specified. Continuous variables will be summarized using descriptive statistics (n, mean, with standard deviation; minimum, first quartile, median, third quartile,

and maximum). Outliers will be included in descriptions as part of presenting ranges and percentiles (25th and 75th). The mean and SD will be rounded to one decimal place.

All statistical tests will be two-sided and at 5% level of significance.

6.2 Missing values

6.2.1 Missing values for non-outcome variables

For descriptive analyses, each variable will be described with frequencies of missing and “Not Known” values. Outliers will be included in description as part of presenting ranges and percentiles (25th and 75th).

In case of partial dates, the following transformations will be made to estimate time frames and durations:

- If only month and year are indicated, “15” will be added for day
- If only year is indicated, “01” will be added for day and “07” for month

If this decision implies negative duration or inconsistencies, it will be reviewed case by case. Otherwise, the date will be considered missing. The possibility of using multiple imputation will be explored, if required during analysis, to address missing data, and subsequently evaluated with sensitivity analyses.

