3.4 Follow-up period

The HCWs will be followed up for 12 weeks upon enrollment in the study.

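### The SAP's partial-date rule covers the dates that set time zero, and its checks can miss a pre-enrolment prophylaxis start imputed months too early

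*SAP*

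**What the plan says.** SAP 6.2.1 opens its date rule for non-outcome variables in general terms: "In case of partial dates, the following transformations will be made to estimate time frames and durations". Two fixed rules follow: "If only month and year are indicated, “15” will be added for day" and "If only year is indicated, “01” will be added for day and “07” for month". Prophylaxis dates are not named, but no date is exempted. SAP 3.6.2 lists prophylaxis start and stop dates among the collected variables.

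Two safeguards follow. The first is "If this decision implies negative duration or inconsistencies, it will be reviewed case by case. Otherwise, the date will be considered missing". The second is tentative: "The possibility of using multiple imputation will be explored, if required during analysis, to address missing data", with later evaluation by sensitivity analysis.

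In the primary model (SAP 6.4.1), controls start the clock at first known exposure to COVID-19 patients. For HCWs who ever take prophylaxis, "their index date will be 7 days after initiation of treatment". On follow-up, SAP 3.4 says: "The HCWs will be followed up for 12 weeks upon enrollment in the study". Neither sensitivity analysis listed in SAP 6.7 varies or excludes imputed dates.

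**The concern.** A mid-month or mid-year default is tolerable for a descriptive history variable. It is a blunt tool for a date that starts the survival clock with a 7-day lag. The rule makes no stated use of the weekly surveys, which can place a start during follow-up within the interval between two reports. For starts before enrolment, the enrolment date gives an upper limit that the rule also does not use.

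Three things depend on these dates: time zero for treated HCWs (and, through first exposure, for controls), the description of use before and after first exposure (SAP 6.3 and 6.3.7), and any treatment duration calculated from start and stop.

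Imprecise dates are foreseeable. The data are self-reported and are not queried after submission (Protocol 8.8.1). Protocol 8.9 acknowledges recall bias, and SAP 6.6 foresees gaps of more than 3 months between index date and enrolment. A partial date will therefore usually be settled by the derivation rule.

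**Working it through.** The plan states no figure for date error, so there is none to reproduce. The check is calendar arithmetic, followed by a test of which errors the safeguards catch.

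**Inputs.** Imputed values: the 15th, or 1 July (SAP 6.2.1). Lag: 7 days (SAP 6.4.1). Follow-up: 12 × 7 = 84 days from enrolment (SAP 3.4). Assumption, not in the documents: true dates are spread evenly over 2020 (366 days).

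**Year-only dates.** 1 July is day 183 of 2020.
- The true date lies between 182 days before and 183 days after the imputed one.
- Mean absolute error = (182×183/2 + 183×184/2)/366 = (16,653 + 16,836)/366 = 91.5 days.
- Off by more than 84 days: (182 − 84) + (183 − 84) = 98 + 99 = 197 of 366, or 53.8%.
- Mean signed error = 183.5 − 183 = 0.5 day.

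**Month-only dates.**
- The true date lies between 14 days before and 16 days after the 15th.
- Mean absolute error = [12×105 + 7×136 + 4×120 + 105]/366 = 2,797/366 = 7.6 days.
- Off by more than 7 days: days 1 to 7 (12×7 = 84) plus days 23 onward (7×9 + 4×8 + 7 = 102) = 186 of 366, or 50.8%.
- Mean signed error = (7×31×16 + 4×30×15.5 + 29×15)/366 − 15 = 5,767/366 − 15 = 0.8 day.

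**What the checks catch.**
- A start imputed too late, so that a recorded infection precedes time zero, gives a negative time. It goes to review.
- A start imputed before a survey that did not report the drug can reasonably be read as an inconsistency. It would probably go to review.
- A pre-enrolment start imputed too early need not trip either check. Take a true start of 20 November 2020, recorded as the year alone, with enrolment on 1 December. The imputed start is 1 July, and 30 + 31 + 30 + 31 + 20 = 142 days early. Time zero becomes 8 July instead of 27 November. All durations are positive and no earlier survey exists to contradict it. If first exposure fell between those two start dates, the drug would also be classed as begun before exposure instead of after it.
- A start and stop in the same month, both without a day, become the 15th and the 15th. The duration is 0, which is not negative.

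**Direction of bias.** In the example, an HCW who stays uninfected gains 142 event-free treated days, which favours the drug. An HCW infected between 8 July and 27 November moves from before time zero to after it and becomes a treated event, which counts against the drug. Both can occur, because HCWs may be infected at enrolment (SAP 3.1) and are excluded only for infection before first exposure (SAP 3.1.1.2).

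**What survey bounds can do.** For a start during follow-up with both weekly surveys completed, the feasible days are 1 to 7 after the last survey without the drug. The midpoint is day 4, so the error is at most 3 days, against 16 under the month-only rule. For the November example, bounds help little: the feasible interval is 1 January to 1 December 2020 (days 1 to 336), with its midpoint at about day 168. The true start is day 325, so the midpoint is 325 − 168 = 157 days early. A year-only, pre-enrolment start cannot be recovered by any point value. Its effect has to be shown by a sensitivity analysis.

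**The case against.** The strongest reply has five parts.

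- **The defaults are midpoints.** Under even spread the signed error is near zero, so the main effect is noise. This stands for the average, but does not make an individual time zero usable when it may be months out.
- **Review already covers inconsistencies.** This stands for late starts that give negative time and, on a fair reading, for starts that contradict an earlier survey. It leaves the early-imputed pre-enrolment start and the zero duration. The review also has no decision rule. The SAP does not say whether it is done with knowledge of infection status.
- **Duration and stopped/ongoing status are collected as separate fields (SAP 3.6.2).** This stands. The duration objective does not rest on imputed dates alone, and a zero can be checked against those fields, though the SAP does not say it will be.
- **Partial dates may be rare.** This stands. No document says whether the form accepts them, and Protocol 8.8.1 describes validation at entry.
- **The 84-day comparison is loose.** This stands. Follow-up runs from enrolment, while time zero may precede it, so 84 days serves only as a scale.

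A reader might infer that the rule makes prophylaxis look protective. The documents do not support that: infections before enrolment can count, early imputation works in both directions, and the number of affected HCWs is unknown. Nor may one take six months as the typical error. It is the maximum for year-only dates.

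**Conclusion.** The point holds as a gap in the date rule that is cheap to close, not as a demonstrated bias. The rule, read by its scope, applies to the dates that set time zero. The largest error is 16 days for month-only dates and 183 days for year-only dates. An early-imputed start before enrolment, and a zero duration from same-month dates, can pass the stated checks. The averages and percentages rest on the assumption of even spread; the maxima and the 142-day example do not. The effect on the hazard ratio, in size or sign, cannot be calculated from the documents. The option of multiple imputation does not settle the matter, because it is not committed. The sentence on treating a date as missing does not say when it applies.

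**What to change.** - **SAP 6.2.1.** For prophylaxis start and stop and for first exposure, replace the fixed values with the midpoint of the feasible interval. That interval is the stated month or year, limited to the period after the last survey without the report and up to the first survey with it. For starts before enrolment, the upper limit is the enrolment date. Require start no later than stop, and check the result against the collected duration and status.
- **SAP 6.2.1.** Carry out any manual date review without sight of infection status. State when a date is set to missing.
- **SAP 6.7.** Add a run of the primary model that excludes HCWs, treated or control, whose time zero rests on a year-only date. Alternatively, set that date to its earliest and then its latest feasible day.
- **Reporting.** Give the number of imputed dates by type, so that the reach of the problem is visible.

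It would be unwise to start year-only pre-enrolment users at enrolment as current users instead. That misclassifies those who had already stopped, and drops their earlier infections while controls, whose clock starts at first exposure, keep theirs.

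The cost is SAP wording, a short derivation program on data already held, and a small number of extra model runs. HCWs with year-only dates are lost from the exclusion version of the sensitivity analysis only.
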